3.4 Early Withdrawal /Discontinuation of the Study Treatment

A participant will be withdrawn from study treatment for any of the following reasons:

- Withdrawal of consent from the study by the participant at any time and for any reason. The reason for elective withdrawal will be documented in the research record if known.
- Unacceptable toxicity in the judgement of the Principal Investigator.
- Toxicity possibly related to abemaciclib does not resolve in14 days.
- Progression of disease requiring alternative systemic treatment.
- Significant participant or protocol noncompliance that, in the opinion of the Principal Investigator, warrants withdrawal of treatment. For example, participant is noncompliant in taking prescribed study medication or fail to return for scheduled follow up visits.
- Development of intercurrent, non-cancer related illnesses or complications that prevent either continuation of therapy or regular follow up.
- In the opinion of the Principal Investigator, it is inappropriate for the participant to continue on the study.
- Best medical interest of the participant at the discretion of the Principal Investigator.
- Subject becomes pregnant.
- Participant become lost to follow up. Participants who are unable to be located despite 3 documented attempts at contact (telephone, mail, or email) followed by a certified letter will be considered lost to follow up and rendered off study.
- Premature study closure.

Every effort should be done to help assure participants who are withdrawn from study treatment undergo the planned end of study follow up, end of treatment follow-up as outlined.3.4.1 Follow-up

An EOT visit will occur 30 ± 7 days from the last study treatment. Follow-up visits will occur every 3 months (\pm /- 7 days) x2, beginning 3 months after last dose of the study drug, then every 6 months (\pm 7 days) thereafter.

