7.1.5 Study Treatment

Abemaciclib will be given as a single oral agent. The starting dose will be 200 mg twice daily. One cycle = 28 days. There will be no protocol scheduled hiatus and daily dosing will be continuous unless there is unacceptable toxicity, disease progression, or death.

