7.3.2 Study drug information

When used as monotherapy, the recommended dose of abemaciclib is 200 mg taken orally twice daily. Continue treatment until disease progression or unacceptable toxicity.

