7.3.8 Dose Delays/Modifications

Dose Modifications for Adverse Reactions

The recommended abemaciclib dose modifications for adverse events are provided in table below. Discontinue abemaciclib for participants unable to tolerate 50 mg twice daily. Once the drug is reduced, there is no dose re-escalation.

Abemaciclib Dose Modification for Adverse Reactions

| Dose Level | Abemaciclib Dose |
|---------------------------|--------------------|
| Recommended starting dose | 200 mg twice daily |
| First dose reduction | 150 mg twice daily |
| Second dose reduction | 100 mg twice daily |
| Third dose reduction | 50 mg twice daily |

Guidelines for Dose Adjustments and Delays of Abemaciclib

| Toxicity Type | Toxicity Profile and Severity | Dose Modification | Dose Reduction |
|--------------------------------------------------|----------------------------------|---------------------------------------------------------|------------------------------------------------------------------------------------------------------------------------------------------|
| Hematologic Toxicity | Grade 3 | Dose MUST be held until toxicity resolves to ≤ Grade 2. | Dose MAY be reduced by 1 dose level at investigator's discretion. |
| Hematologic Toxicity (second or more recurrence) | Grade 3 | Dose MUST be held until toxicity resolves to ≤ Grade 2. | Dose MUST be reduced by 1 dose level with each occurrence. Discontinue abemaciclib for participants unable to tolerate 50 mg twice daily |
| Hematologic Toxicity | Grade 4 | Dose MUST be held until toxicity resolves to ≤ Grade 2. | Dose MUST be reduced by 1 dose level. Discontinue abemaciclib for participants unable to tolerate 50 mg twice daily |

| Nonhematologic Toxicity (except diarrhea and ALT increased) | Persistent or recurrent Grade 2 that does not resolve with maximal supportive measures within 7 days to baseline or Grade 1 | Dose MUST be held until toxicity resolves to either baseline or ≤ Grade 1. | Dose MUST be reduced by 1 dose level. Discontinue abemaciclib for participants unable to tolerate 50 mg twice daily |
|----------------------------------------------------------------------|-----------------------------------------------------------------------------------------------------------------------------|----------------------------------------------------------------------------|-----------------------------------------------------------------------------------------------------------------------------|

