| Nonhematologic Toxicity (except diarrhea and ALT increased) | Grade 3 or 4 that does not resolve with maximal supportive measures within 7 days to baseline or Grade 1 | Dose MUST be held until toxicity resolves to either baseline or ≤ Grade 1. | Dose MUST be reduced by 1 dose level. Discontinue abemaciclib for participants unable to tolerate 50 mg twice daily |
| Diarrhea | Grade 2 that does not resolve within 24 hrs to at least Grade 1 | Dose MUST be held until toxicity resolves to \(\leq \text{Grade} \) 1. | Dose MAY be reduced by 1 dose level. |
| Diarrhea | Grade 3 or 4 that does not resolve with maximal supportive measures within 7 days or requires hospitalization. | Dose MUST be held until toxicity resolves to ≤ Grade 1. | Dose must be reduced by 1 dose level - Discontinue abemaciclib for participants unable to tolerate 50 mg twice daily |

| ALT/AST increased | Grade 2 (>3.0-5.0xULN) that does not resolve within 7 days to baseline or < Grade 1 | Dose MUST be held until toxicity resolves to baseline or Grade 1 | Dose MUST be reduced by 1 dose level |
|-------------------|-------------------------------------------------------------------------------------|------------------------------------------------------------------|------------------------------------------|
| | Grade 3 (>5.0-20.0xULN) with total bilirubin >2xULN, in the absence of cholestasis | Abemaciclib therapy MUST be discontinued | Abemaciclib therapy MUST be discontinued |
| | Grade 4 (>20.0xULN) | Abemaciclib therapy MUST be discontinued | Abemaciclib therapy MUST be discontinued |

Abbreviations: ALT = alanine aminotransferase, AST=aspartate aminotransferase, ULN = upper limit of normal.

Monitor ALT, AST, and serum bilirubin prior to the start of abemaciclib therapy, every 2 weeks for the first 2 months, monthly following cycle 2, and as clinically indicated.

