7.4.4 General Guidance for Hematology Toxicity

7.4.4.1 Neutropenia

Severe (Grade 3 and 4) neutropenia was observed in participants receiving abemaciclib-see Tables 1-4. If a participant requires blood cell growth factors, these should be administered according to ASCO Guidelines. Abemaciclib must be held for at least 48 hours after the last dose of blood cell growth factors is administered and until toxicity resolves to at least Grade 2. When abemaciclib is resumed, the dose must be reduced by 1 dose level unless already performed for incidence of toxicity that led to the use of growth factor.

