7.4.5 General Guidance for Interstitial lung disease (ILD)/Pneumonitis events

Interstitial lung disease (ILD) / pneumonitis has been identified as an adverse drug reaction for abemaciclib. Adverse events reported included events such as interstitial lung disease, pneumonitis, obliterative bronchiolitis, organizing pneumonia, pulmonary fibrosis. The majority of events were Grade 1 or Grade 2 with serious cases and fatal events reported.

Monitor for clinical symptoms or radiological changes indicative of ILD/pneumonitis and please ask patients to report any new or worsening pulmonary symptoms. Symptoms may include hypoxia, cough, dyspnea, or interstitial infiltrates on radiologic exams.; these symptoms should be investigated and treated as per local clinical practice and/or guidelines (including corticosteroids as appropriate). Infectious, neoplastic, and other causes for such symptoms should be excluded by means of appropriate investigations. Investigations may include imaging such as high resolution computer tomography (HRCT), bronchoalveolar lavage (BAL), and biopsy as clinically indicated (see also Table 7: refer to dose adjustment table for interstitial lung disease/pneumonitis).

Dose Modification and Management — Interstitial Lung Disease/Pneumonitis

| ose mounication and managem | ent interstitut Eung Disease/I neumonitis |
|--------------------------------------------------------------------------------------------------------------------------------------|--------------------------------------------------------------------------------------|
| CTCAE Grade | Abemaciclib Dose Modifications |
| Grade 1 or 2 | No dose modification is required. |
| Persistent or recurrent Grade 2 toxicity that does not resolve with maximal supportive measures within 7 days to baseline or Grade 1 | Hold dose until toxicity resolves to baseline or Grade 1. Resume at next lower dose. |
| Grade 3 or 4 | Discontinue abemaciclib. |

Dose Modification and Management — Nonhematologic Toxicities Excluding Diarrhea, ALT Increased, and ILD/Pneumonitis

| CTCAE Grade | Abemaciclib Dose Modifications |
|---------------------------------------------------------------------------------------------------------------------------------------------------|---------------------------------------------------------------------------------------|
| Grade 1 or 2 | No dose modification is required. |

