8.0 STATISTICAL PLAN

This is a pilot study to confirm tolerability of abemaciclib and provide an estimate of the overall response rate. A sample size of 10 subjects is determined to be minimally sufficient for these pilot study objectives. The primary objective of this study is objective response rate in locally advanced and metastatic biliary tract carcinoma that have failed (tumor progression or patient intolerance) one or more lines of systemic therapies. All participants will be treated with 200 mg twice daily of oral abemaciclib for 28 days being one cycle. Participants will be treated up to 8 cycles or until progression, untoward toxicities or death. Antitumor activities will be evaluated using RECIST v1.1.

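### Section 3.4 requires withdrawal for any possibly related toxicity unresolved at 14 days, with no grade or recovery level, which conflicts with dose rules that keep some of those participants on drug

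*Combined protocol and SAP*

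**What the plan says.** Section 3.4 lists reasons for which a participant will be withdrawn from study treatment. Any one is sufficient, and one of them is "Toxicity possibly related to abemaciclib does not resolve in14 days". Toxicity that the principal investigator judges unacceptable is a separate bullet, so that judgement does not limit the 14-day bullet. The bullet does not refer to the dose tables.

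The dose rules are graded:

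- **Nonhematologic Grade 1 or 2 (7.4.5):** "No dose modification is required". The exception is Grade 2 that persists or recurs and does not settle to baseline or Grade 1 within 7 days of maximal supportive care. That is held, then resumed one level lower.
- **Hematologic Grade 3 or 4 (7.3.8):** "Dose MUST be held until toxicity resolves to ≤ Grade 2", after which dosing may continue, in some rows at a reduced dose.
- **Neutropenia treated with growth factor (7.4.4.1):** the drug is held for at least 48 hours after the last growth-factor dose "and until toxicity resolves to at least Grade 2".
- **Diarrhea (7.3.8):** one hold trigger is "Grade 2 that does not resolve within 24 hrs to at least Grade 1". Dosing can resume at Grade 1 or lower.
- **Other nonhematologic toxicity (7.3.8, 7.4.5):** dosing resumes at baseline or Grade 1. Grade 3 or 4 ILD/pneumonitis, Grade 4 ALT/AST, and Grade 3 ALT/AST with bilirubin above twice the upper limit and no cholestasis require discontinuation.

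None of the hold rows states a maximum duration. The general statements on treatment duration are "daily dosing will be continuous unless there is unacceptable toxicity, disease progression, or death" (7.1.5), "Continue treatment until disease progression or unacceptable toxicity" (7.3.2) and "Participants will be treated up to 8 cycles or until progression, untoward toxicities or death" (8.0).

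**The concern.** Two mandatory sets of instructions give different answers for the same participant. Someone with a mild, possibly related event that lasts more than two weeks is told by 7.4.5 to carry on and by 3.4 to stop. Someone who recovered enough to restart under the dose tables may face the same contradiction.

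Staff would have to choose. Following 3.4 stops people who tolerate the drug. Following the dose tables departs from a mandatory withdrawal rule. Deciding case by case mixes the two. Section 8.0 says the pilot is meant to confirm tolerability, and 8.5.2 tabulates adverse events leading to withdrawal. If that count includes people withdrawn for a mild event under 3.4, it no longer describes how well the drug is tolerated.

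**Working it through.** The documents state no figure that depends on this rule, so there is none to reproduce. The check sets the 3.4 bullet beside the dose rules, case by case. The days used are illustrative.

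| Case at day 15 | Dose rules | 3.4 bullet | Result |
|---|---|---|---|
| A. Possibly related Grade 1 fatigue, unchanged since onset | Full dose continues (7.4.5) | Not resolved: withdraw | Conflict on the words |
| B. Nonhematologic Grade 2 that fell to Grade 1 within 7 days and stays there | Full dose continues (7.4.5) | Withdraw, read literally | Conflict on the words |
| C. Grade 3 neutropenia held, down to Grade 2 on day 8, dosing resumed, still Grade 2 | Dosing continues (7.3.8; also 7.4.4.1 if growth factor was given) | Depends on what *resolve* means | Conflict only if it means full recovery |
| D. Grade 3 diarrhea held, down to Grade 1, dosing resumed at a lower dose | Dosing continues (7.3.8) | Same as C | Same as C |
| E. Grade 3 nonhematologic event still on hold and above Grade 1 | Hold continues, no time limit (7.3.8) | Withdraw | No contradiction: 3.4 supplies a limit the tables lack |
| F. Grade 3 or 4 ILD, or the specified ALT/AST rises | Discontinue (7.3.8, 7.4.5) | Nothing added | No conflict |

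**Cases A and B.** In A the event has not improved at all, so it has not resolved in any ordinary sense. The tables set no recovery level for an event that needs no hold, so there is none to carry over into 3.4. B is the same once the event has settled at Grade 1.

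**Cases C and D.** The answer depends on one word. The dose tables use *resolve* with a grade attached. Section 10.1.2 instead treats an event that resolves as different from one that improves to baseline or Grade 1, which supports full recovery, but it governs follow-up of adverse events ongoing at the end-of-treatment visit, not dosing. The bullet gives no grade and no definition, so both readings remain open.

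**Clock start.** For nonhematologic Grade 3 or 4 events, 7.3.8 requires the hold only after 7 days without resolution. The 14 days could therefore end at either of two points:

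- Clock from onset: day 14.
- Clock from the hold: 7 + 14 = about day 21 from onset.

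The choice moves a safety limit by about 7 days, and 3.4 does not make it.

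**Number affected.** This would be the treated participants multiplied by the share with a possibly related event that lasts beyond 14 days and needs no hold or has reached the resumption grade. The documents give frequencies and grades by event type but no durations. That share cannot be calculated, and no range narrower than none to all treated follows from the text.

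**The case against.** The strongest reply is that *resolve* is a graded word throughout the dosing text, so the 3.4 bullet is naturally read as a 14-day limit on recovery to the dose-table level. On that reading cases C and D disappear, and few investigators would withdraw someone for lasting Grade 1 fatigue. As to intent, that is plausible, and it is why the recovered-event part of this point is conditional. It does not remove case A. The bullet is mandatory, sits apart from the investigator's judgement, and has no grade floor. The discretionary bullets in 3.4 add reasons to withdraw and waive none. Even on the milder reading, staff using the tables would not see the 14-day limit.

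A reader might infer four stronger points that the documents do not support:

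- **That every long hold contradicts 3.4.** The hold rows are silent on duration, so 3.4 fills a gap.
- **That treatment elsewhere stops only for progression, death or unacceptable toxicity.** Sections 7.1.5, 7.3.2 and 8.0 read that way, but there are specific stops too: inability to tolerate 50 mg twice daily, the ALT/AST and ILD rules, suspected drug-induced liver injury (10.1.1) and pregnancy (10.4). None of them covers a lasting Grade 1 event as such or an event recovered to the resumption grade.
- **That the rule costs response-rate evaluability or the target of 10.** Section 7.0 requires two cycles and excepts only rapid progression. But it also asks for end-of-treatment scans when participants with measurable disease stop off schedule, 8.2.3 counts treated participants without a post-dose assessment as non-responders, and 7.1.7 does not offer replacement for inability to tolerate treatment. How toxicity withdrawals enter the response analysis is a separate question that this bullet does not create.
- **That the effect can be sized from other figures.** In the cited breast cancer study at 200 mg twice daily (2.4.2), 8% discontinued for adverse reactions and 49% had dose reductions. Those figures say nothing about duration or about a 14-day rule. That one withdrawal among 10 to 20 treated is 5% to 10% is true of any single event.

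**Conclusion.** The concern holds in a limited form. Taken literally, 3.4 conflicts with 7.4.5 for nonhematologic Grade 1 and non-persistent Grade 2 events. It also conflicts with 7.3.8, 7.4.4.1 and 7.4.5 for participants who have resumed dosing at a permitted grade, but only on the assumption that *resolve* means full recovery, which the text neither states nor excludes.

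The consequence is that tolerating participants could be withdrawn and counted under adverse events leading to withdrawal. Its size is unknown and cannot be estimated from the documents. No effect on response rate or on reaching 10 evaluable participants is claimed. The severity is minor to should-fix: the conflict is real, it touches a tolerability output, and it is cheap to remove.

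**What to change.** Amend the 3.4 bullet so that it applies only to possibly related toxicity that requires a dose hold under 7.3.8, 7.4.4.1 or 7.4.5 and has not recovered, within 14 days, to the grade at which that section permits dosing to resume. Add a sentence saying that events needing no dose modification, and events already recovered to the resumption grade, do not trigger withdrawal. Cross-reference the 14-day limit in the 7.3.8 and 7.4.5 tables and in 7.4.4.1, so that staff working from those sections see it. Leave the immediate-discontinuation rules for ILD and ALT/AST unchanged.

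The sponsor-investigator must state whether the 14 days run from onset or from the start of the hold. This is more than editorial: a hold-based clock could allow about 21 days from onset for nonhematologic Grade 3 or 4 events, which may be looser than intended. An onset-based clock avoids that but leaves about 7 days of hold for those events.

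The cost is amendment wording and that one safety decision. No visits, procedures or participants are added.

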4.0 RECRUITMENT METHODS

4.1 Identification/Screening of Subjects

Patients seen at Penn State Cancer Institute with the disease of study may be pre-screened through the electronic medical record or in the clinic by research team members for basic variables such as age and ability to sign consent. Those patients deemed by this pre-screening effort to meet these basic criteria will be approached for consideration of participation.

This clinical trial will be available for potential patient candidates to view on clinicaltrials.gov.

Formal screening for participation will not be initiated until an IRB approved informed consent form has been signed. All subjects who sign consent will be assigned a study ID number.

Subjects who consent to participate in the clinical trial but who are not subsequently assigned to the study intervention or registered will be considered screen failures. Subject may be re-screened. All re-screened subjects will be assigned the same subject ID number as was assigned during the initial screening.

4.2 Recruitment Process

Potential participants will be approached for possible participation in the PSCI outpatient clinic or the inpatient setting if applicable. The protocol may be initially presented to the patient by the Principal Investigator or Sub-Investigator. A member of the study team will discuss the protocol further with the patient.

4.3 Recruitment Materials

No recruitment materials will be used for the purpose of this clinical trial.

5.0 CONSENT PROCESS AND DOCUMENTATION

5.1 Informed Consent Process

The informed consent process will be carried out in compliance with federal regulations. A copy of the signed IRB approved consent document will be provided to the patient. The original document will be maintained in the protocol specific regulatory files with copies in the Cerner electronic medical record and research chart.

5.2 Coercion and Undue Influence

During the consent conference, all patients will be made aware that this is a research investigation and participation is optional. Their medical care at Penn State Health will not be affected by their decision to participate or not participate.

5.3 Consent Other Considerations

5.3.1 Non-English-Speaking Participants

Non-English-speaking patients are eligible for participation in this trial. Protocol and related information will be provided to the patient orally in their language using a certified interpreter prior to and throughout the course of the study. In the event that a non-English speaking patient is identified, the consent process and ongoing research process will be carried out in compliance with federal regulations, as well as the following institutional policies and procedures.

5.3.2 Cognitively Impaired Adults/Unable to consent

Not applicable. Eligibility requires that patients are able to understand the requirements for the study and provide consent themselves.

6.0 HIPAA RESEARCH AUTHORIZATION AND/OR WAIVER OR ALTERATION OF AUTHORIZATION

| 6.1 | | Authorization and/or Waiver or Alteration of Authorization for the Uses and Disclosures of PHI. Check all that apply: | | | |
|-----|-------------|------------------------------------------------------------------------------------------------------------------------------------------------------------------------------------------------------------------------------------------------|--|--|--|
| | | Not applicable, no identifiable protected health information (PHI) is accessed, used or disclosed in this study. [Mark all parts of sections 6.2 and 6.3 as not applicable] | | | |
| | \boxtimes | Authorization will be obtained and documented as part of the consent process. [If this is the only box checked, mark sections 6.2 and 6.3 as not applicable] | | | |
| | | Partial waiver is requested for recruitment purposes only (Check this box if patients' medical records will be accessed to determine eligibility before consent/authorization has been obtained). [Complete all parts of sections 6.2 and 6.3] | | | |
| | | Full waiver is requested for entire research study (e.g., medical record review studies). [Complete all parts of sections 6.2 and 6.3] | | | |
| | | Alteration is requested to waive requirement for written documentation of authorization (verbal authorization will be obtained). [Complete all parts of sections 6.2 and 6.3] | | | |
| 6 | 5.2 W | Vaiver or alteration of authorization statements of agreement | | | |
| | N | ot applicable. | | | |

